Misattribution of symptoms to a residual TBI when such symptoms are secondary to stress, chronic sleep deprivation, Post-Traumatic Stress Disorder (PTSD) or other factors can iatrogenically reinforce the misconception that these symptoms are permanent.³⁵

A growing body of literature demonstrates the role of expectation in both cognitive performance and rate of symptom complaint. Simply drawing attention to the label "TBI" can cause increased symptom reporting and result in poorer cognitive performance.³⁶⁻³⁸ If there is an expectation of post-injury problems, then in at least some individuals, such symptoms are more likely to occur.^{37 39} In addition, since virtually everyone with a mild TBI experiences acute symptoms for minutes to hours, the mere presence of these symptoms can reinforce preexisting expectations and beliefs. In contrast, if there is no expectation of ongoing symptoms, then few or no ongoing

symptoms are reported.³⁶ Both brain dysfunction and expectation play independent and interactive causative roles.⁴⁰ Given the current political climate and the emphasis on TBI as the "signature injury" of the war on terror, research regarding patient self-expectation is particularly pertinent. Merely by screening individuals within the context of increased media attention on TBI, the stage is set for expectancies to exert an influence on the patient's belief system and to attribute many or all difficulties to TBI. In addition, there may be an inclination by the patient to attribute symptoms to TBI, rather than psychological diagnoses such as PTSD, given the perception that a physical brain injury is less "their fault" or under their control.

Figure 1. Theoretical Model of PCS

A Theoretical Model of PCS. Based on a thorough review of PCS literature, we posit a theoretical model of acute and chronic symptom etiology and maintenance, as depicted in Figure 1.⁴⁰ Factors that are likely most modifiable are shaded light gray.

Providing Education to Reduce PCS in Civilians -

Psychoeducational interventions

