Q2: What are the moderators and mediators of the effectiveness of Concussion Coach?

- (a) Is comfort with technology related to efficacy of Concussion Coach?
- (b) Is perceived social support related to efficacy of Concussion Coach?

Q3: Does use of Concussion Coach (a) increase Veterans' knowledge about TBI and change Veterans' attribution of symptoms from mild TBI to less "pathological" explanations (e.g., stress, post-deployment re-adjustment, or other causes), (b) increase Veterans' self-efficacy in coping with symptoms?

More broadly, are the effects of Concussion Coach on PCS and psychological distress mediated through change (from T1 to T2) in Veterans' perceptions and knowledge of the illness and in self-efficacy?

Q4: What aspects of Concussion Coach are most associated with positive outcomes among recipients of Concussion Coach? Is more frequent use of specific components of Concussion Coach associated with greater improvement, relative to other components?

Q5: What are the factors associated with use of Concussion Coach or with deriving benefit from use of Concussion Coach that can be used to inform future modifications of the application and wide scale implementation?

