5.0 Study Procedures

5.1 Study Design

- Describe experimental design of the study. Include sequential and/or parallel phases of the study, including durations, and explain which interventions are standard of care.
- Include a description of how anticipated risk will be minimized and include an analysis of risk vs. potential benefit.
- Provide description of the study population (delineate all categories of subjects – patients, providers, family members, employees, etc.). Include anticipated enrollment numbers
- As applicable, provide information on any added protections for vulnerable populations.
- If applicable include information on data.

Patients who meet eligibility criteria and consent to participate in the study are randomly assigned to one of two arms, either the Concussion Coach group, which will receive the Concussion Coach "Explorer" version either downloaded onto their own smart phone or via an iPod touch® given them for this purpose or the no mobile app control group. Study personnel will explain the purpose of the study, complete the informed consent process in person or over the telephone, obtain the random treatment assignment and introduce the participant to his/her baseline evaluator, if appropriate. The random assignment to intervention will be accomplished in blocks within each site. While small block sizes allow intervention group sizes to be very similar it may make the allocation process predictable. Therefore, to reduce selection bias and achieve balance across the intervention arms, a sequence list of individual assignments by random block sizes will be generated.

Both groups will be assessed in a pre/post intervention design and will be compensated for completing study questionnaires. During the time that they are involved in the study, the intervention group will be sent (via Concussion Coach) reminders to engage with the App. Their use (e.g., total time spent on each component of the App) will be collected electronically. Both

Version:13 05/31/2018

groups will receive care as usual (meaning their regularly scheduled VA appointments and medications). At the completion of the study, both groups will be encouraged to download the App for their own use, with assistance from the study team if needed (see Figure 2).

Description of Intervention & Training

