Data Collection Methods: After informed consent and randomization, participants will complete baseline study measures. At follow-up, participants will be re-assessed using the same measures via mail, telephone or in person with telephone reminders, if needed. In addition, Concussion Coach will also collect the extent of their interaction with the application during their participation.

Individual interviews will be conducted with at least 10% of the Concussion Coach users to evaluate their perception and satisfaction with other TBI-related education received within the VA to date, their overall satisfaction with Concussion Coach e.g. its ease of use, perceived barriers and facilitators to the use of the App, behavioral intention to use Concussion Coach in the future and recommendations for improving it. This 10% sample will not be random – rather we will solicit interviews from those who improved using PCS Concussion Coach, those who did not get better or became worse, and those who did not use the App during the study period or used it infrequently. In addition to qualitative questions about barriers and facilitators, interview questions will include quantitative assessment of satisfaction (e.g., rating scales of satisfaction). Interviews will be conducted by experienced trained interviewers (e.g., [name]) and will be audio recorded. Participants will already be consented in person or over the telephone, so the interviewer will identify and briefly recap the consenting process, the project, and then ask permission for audio tape recording the interview. Interviews will be conducted by phone or in person based on participant convenience. The interviewer will use standard communication techniques to stimulate discussion such as generic prompts (tell me more), summarizing statements, silence, and eye contact. If the respondent exhibits adverse reactions, such as shame, during the interview, every effort will be made to encourage him or her and they will be reminded of their rights as participants.

Risk Minimization Plan:

The educational program is self-administered and participation is strictly voluntary. There are no known risks involved. The PI will inform participants of all methods used to maintain confidentiality of information. Participants will be assured of the confidentiality of the data and that no one outside of the research team will have access to the raw data.

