It is possible that potential participants will not be able to meet in person and will need to talk to a study investigator via telephone. In this instance, a study investigator will explain the study determine that the participant is interested in participating, and screen for eligibility. If eligible, an appointment will be scheduled for the participant to meet in-person with the study team members to complete the consenting process. Or, for interested participants who reside a distance away from the VA and would like to participate in the study the ICF will be done over the telephone. After the Telephone Consent process is complete, a copy of the study ICF/Information Sheet will be mailed to the participant for his/her file. Once the consent process is completed via telephone with those participants who are not able to physically be at either the Tampa or Bay Pines VA site location, they will be asked to complete the study Baseline questionnaires. When speaking to potential participants via telephone, the study team member will be physically located at the Tampa or Bay Pines VA.

To facilitate the recruitment process, we will hang flyers throughout the hospitals and catchment area (e.g., outpatient clinics) of each hospital, and provide the clinical team with hospital-based flyers and business cards to give to interested patients. (See the Appendix for the hospital-based flyer and business card.)

Relevant Veteran Events: With permission from event organizer(s) and/or department manager(s), we will attend and/or contribute to relevant events around the Tampa/St. Petersburg area. Methods of recruitment during events may include but are not limited to, providing flyers, cards, and/or give-away recruitment materials. It may also involve giving a short presentation on the participation opportunities, collecting contact information from interested participants, or leaving a basket of give-away recruitment materials at a desk for interested participants to pick up at their leisure (the flyers, business cards, and give-away recruitment

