All data will be combined into a study database. The integrity of the database will be managed by our database manager. Analyses will be conducted by the statistician ([name]) and the PI ([name]).

Data Analysis Plan: An intention-to-treat (ITT) analysis will be performed, that is analysis will be based on the groups to which participants are randomized regardless of whether they receive or adhere to the assigned intervention. This will allow us to test the effects of assigning TBI Coach in practice, separate from assessing effects of adherence and/or loss to follow-up. Those who are lost to follow-up and therefore are missing outcome measures (T2 assessments) will be included in separate comparison analyses that utilize multiple imputations of the missing data.

For each primary outcome and other measures consisting of multiple items, a summation score will be produced for each subject. Summary of each variable by intervention group will be cross-tabulated. The time spent on TBI Coach and its specific components on the average will also be tabulated. All primary outcomes will be analyzed as continuous variables. Exploratory bivariate plots will be used to investigate possible nonlinear relationships between baseline/covariates and each follow up outcome variable. In separate statistical models proposed, we will control for demographics and other covariates including the baseline values of the outcome under investigation. Where appropriate, nonlinear regression model will be utilized (e.g., generalized additive model).

Hypothesis 1 (Primary Hypothesis): Patients randomized to receive TBI Coach for 3 months will have (a) lower post-concussive symptom severity and (b) lower psychological distress, compared to patients randomized to a no intervention control group, after adjusting for baseline severity and other potential confounders.

Analysis: The two intervention groups (TBI Coach = 1; Control = 0) will be compared on each outcome (a) and (b) in separate regression models that include the group variable and control for the outcome at baseline and other potential confounders. A significant positive estimated coefficient of the group variable will indicate positive TBI Coach's effects on the outcome, with the standardized value of the coefficient as the standardized effect size.

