Hypothesis 2: The effects of TBI Coach on PCS (and psychological distress) will be greater for Veterans who have (a) greater comfort with technology at baseline than for those who are less comfortable; (b) greater social support at baseline than for those with less social support.

Analysis: Two separate tests of moderated effects of TBI Coach will be performed with respect to each outcome. Each regression model in H1 (one per outcome) will be extended by adding a 2-way interaction term (between intervention and (a) eHealth Literacy Scale and (b) Social Support score; one at a time (i.e. two different moderation models per outcome). A significant coefficient of an interaction term will indicate presence of interactive effects. A co-plot using model fitted values will also be produced to further investigate the nature of any significant interaction.

Hypothesis 3: If TBI Coach improves Veterans' (a) knowledge about TBI and attribution of symptoms and/or (b) self-efficacy in coping with symptoms, Veterans will have less PCS and Psychological Distress.

Analysis: Single-mediator models⁷³ will test the indirect effects of the group variable (TBI Coach) on each outcome (separately) with respect to mediating variables: (a) knowledge and attribution, and (b) self-efficacy. Preliminary regression analyses will test whether (1) TBI Coach substantially changes the mediating variable, and (2) the mediating variable changes the outcome. Next, we will proceed to a full mediation model with simultaneous estimation of both direct and indirect effects of TBI Coach on the outcome. The mediated effect will be estimated as a product of the two path coefficients alpha and beta in the indirect pathway. The distribution of the product of coefficients is non-normal and this has implications for statistical inference as well as power calculation (see section on sample size justification). Therefore, the analysis will

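### Randomisation precedes the self-reported baseline forms and nothing available withholds the arm until they are done, so the T1 values used in Hypotheses 1 and 2 could be reported with knowledge of the arm

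*Combined protocol and SAP*

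**What the plan says.** The data collection paragraph of section 5.1 states: "After informed consent and randomization, participants will complete baseline study measures". The design paragraph of the same section gives the same order independently: after consent, staff "obtain the random treatment assignment and introduce the participant to his/her baseline evaluator, if appropriate". The comparison is between the app "or the no mobile app control group".

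Section 5.2 describes a telephone route. After telephone consent, remote participants are told that "they will be asked to complete the study Baseline questionnaires", but the step at which they are randomised is not given.

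The T1 values are then used as follows.
- **Hypothesis 1** (section 5.6): the regressions "control for the outcome at baseline and other potential confounders".
- **Hypothesis 2** (section 5.6): the moderators are T1 scores. The effect is expected to be larger for those with "greater comfort with technology at baseline than for those who are less comfortable", and likewise for social support.
- **Hypothesis 3**: the analysis text in 5.6 does not name T1 mediator values. The link rests on research question 3 in section 2.0, which asks about mediation through change between T1 and T2.

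Section 2.0 also says: "A growing body of literature demonstrates the role of expectation in both cognitive performance and rate of symptom complaint".

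**The concern.** A baseline covariate is safe to adjust for because assignment cannot have influenced it. A self-rated score collected after assignment loses that guarantee if the participant knows the arm. With an app and a no-app arm, anyone told the assignment knows the arm, and the NSI, BSI-18 and PCL-5 are all self-rated (section 5.5). If knowing the arm changes what people report at T1, adjusting for T1 can bias a comparison that randomisation would otherwise have kept fair, and baseline moderators or change scores built on T1 can be distorted too. The random block sizes in section 5.1 guard against guessing the next allocation. They do not address disclosure before the forms are filled in.

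**Working it through.** **Order of steps.** Two statements in section 5.1 agree that assignment comes before the baseline forms. Neither says when the participant is told the arm. Section 5.2 leaves randomisation unplaced on the telephone route. No available text masks the participant or the baseline evaluator, or delays disclosure. Text around section 1.0 and between sections 5.3 and 5.4 was not available.

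**Inputs from the plan (section 5.6).** N = (20 × 33 + 150) × 0.60 × 0.80 = 388.8, stated as 388. Two-sided alpha is 0.05. Covariate R-squared is 0.20.

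**Assumptions, not in the plan.** Equal arms of 194, no true effect, unit SDs, and T1 carrying all of the R-squared, so the slope is √0.20 = 0.447, taken as 0.45. An arm-induced shift d of 0.05, 0.10 or 0.20 SD is assumed and has no source in the documents.

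**Formulas.** The adjusted difference is (T2 difference) − slope × (T1 difference). SE = √(2(1 − slope²)/194) = √(2 × 0.7975/194) = 0.0907. Rejection rates come from the noncentral t with 385 df.

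| Scenario, slope 0.45 | Size of bias | d = 0.05 | d = 0.10 | d = 0.20 |
|---|---|---|---|---|
| Shift at T1 only | 0.45d | 5.7% | 7.9% | 16.8% |
| Same shift at T1 and T2 | 0.55d, opposite sign | 6.1% | 9.3% | 22.7% |
| Clean T1, shift at T2 only | d | 8.5% | 19.6% | 59.5% |

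With slope 0.3 (SE 0.0969), the T1-only row becomes 5.3%, 6.1% and 9.5%.

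**Dropping the T1 covariate.** SE = √(2/194) = 0.1015, which is 1/√(1 − 0.45²) = 1.12 times the adjusted SE. The minimum detectable effect at 80% power, 2.80 × SE, goes from 0.254 to 0.284 SD. Under a T1-only shift the rejection rate is 5.0%. Under a shift that persists at T2 it is 7.8%, 16.6% and 50.2%.

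**Reach of a reordering.** The Abstract reports 419 enrolled, 93% of the goal: 419/0.93 ≈ 451, leaving 32. Section 5.2 gives approximately 600, leaving 181. The shares already enrolled are 419/451 = 0.929 and 419/600 = 0.698. With only that share exposed at T1, the bias is 0.45 × share × d for a T1-only shift, and (1 − 0.45 × share) × d for a persistent one.

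| N = 388, slope 0.45 | d = 0.10 | d = 0.20 |
|---|---|---|
| T1-only, present order | 7.9% | 16.8% |
| T1-only, 32 or 181 reordered | 7.5% or 6.4% | 15.1% or 10.6% |
| Persistent, present order | 9.3% | 22.7% |
| Persistent, 32 or 181 reordered | 9.8% or 11.7% | 24.9% or 32.6% |

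The reordering helps in the first case and hurts in the second, because an equally shifted T1 partly cancels a shifted T2. N is held at 388 throughout. With the plan's 20% attrition, 451 enrolled would give about 361 analysed (451 × 0.80) and 600 would give 480, so the decimals should not be over-read.

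**The case against.** Several objections have force.

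- **Disclosure is not shown.** Staff obtaining an assignment is not the same as the participant hearing it, and unavailable text near the consent section could settle the timing. This stands: what is documented is the order of steps and the absence of any stated safeguard.
- **The expectation passage in section 2.0 is about something else.** It concerns the TBI label and expected post-injury problems, which apply to both arms. It does not say that being allocated an app changes answers before the app is used. This stands. The passage makes a reporting effect plausible and no more.
- **An NSI exists from screening.** Section 5.4 uses the NSI for eligibility, so a score from before randomisation may be available. Nothing makes it the T1 value, the criterion can be met on two items without a total, and it covers none of the other scales. It may limit the problem for the primary outcome but does not remove it.
- **Little enrolment remains, and reordering can backfire.** Both are right, as the figures show, and they argue against reordering as the leading remedy.

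A reader might infer that participants did know their arm at T1, or that Hypothesis 1 is biased in favour of the app. The documents support neither. Higher T1 reports in the app arm would favour the app, higher reports in controls would work against it, and nothing indicates which, if either, occurs.

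**Conclusion.** The concern holds in a limited form. The stated order lets T1 be reported with knowledge of the arm, no available text prevents it, and T1 is the covariate in Hypothesis 1 and the source of the moderators in Hypothesis 2. The link to Hypothesis 3 is weaker. For an assumed shift of 0.05 to 0.20 SD at slope 0.45, the false-positive rate would be about 6% to 17% if the shift is confined to T1, and about 6% to 23% if it persists at T2. These rates depend on a shift the documents do not quantify and on T1 carrying the whole planning R-squared. Steeper slopes would give larger T1-only figures but lie outside the plan's own assumption.

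It is also tempting to read a clean T1 as a cure. It is not: with clean T1 and a 0.20 SD shift at T2 alone, the rate is 59.5%. Open-label reporting at T2 is a separate problem. The point should be fixed, with high confidence in the order of steps and medium confidence that the arm was known at T1.

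**What to change.** 1. **For everyone, before analysis.** Keep the T1-adjusted model as primary. In section 5.6, prespecify a supportive Hypothesis 1 analysis for each outcome without the T1 covariate. For the NSI, add one that uses the eligibility total where it was recorded before randomisation and within a maximum age fixed in advance. State that the model without T1 is immune to a T1-only shift but carries the full shift if it persists at T2, so disagreement between models is reported and not resolved in favour of either. Report, for the in-person and telephone routes, when the arm was disclosed relative to T1.
2. **For remaining enrolments.** Amend sections 5.1 and 5.2 so that all baseline forms are completed before the assignment is obtained or revealed, place randomisation explicitly on the telephone route, and record the order for each participant.

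**Costs.** Step 1 adds one supportive model per outcome (two for the NSI) and a date check; the model without T1 is less precise, as shown above. Step 2 uses existing procedures but leaves two T1 regimes in the data, and its opposite effects under the two scenarios should be stated alongside it. The supportive analyses cover Hypothesis 1 only. For Hypotheses 2 and 3 among those already enrolled, report the limitation.

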5.2 Recruitment Methods

- State how many subjects will be needed.
- Describe when, where, how and by whom potential subjects will be identified and recruited.
- Describe materials that will be used to recruit subjects, e.g., advertisements. Include materials as an appendix or separate attachment.
- Describe any payments to subjects, including the amount, timing (at the end of the study or pro-rated for partial study participation), method (e.g., direct deposit or check), and whether subjects will experience a delay in receiving the payment.

Study Population: Approximately 600 patients with a history of mild TBI and current symptom complaints will be recruited. Participants will be recruited from both the Tampa VA (lead site) and the Bay Pines VA, which is located about 20 miles from the Tampa VA within VISN 8, and their respective outpatient clinics (CBOCs). Both sites are Polytrauma Network Sites (PNS) which are designated sites within the VA Polytrauma System of Care that assess TBI outpatients and see the majority of mild TBI patients.

To ensure that we capture a broad spectrum of Veterans with a history of mild TBI, we will also supplement recruitment from the VA with several methods aimed at recruiting potential community-based TBI participants. Primary recruitment will be through TBI-relevant clinics at both Bay Pines and Tampa VAs. Both facilities have active PNS clinics (Polytrauma Network Sites), Post-Deployment, PTSD and other clinics with patients identified to have a history of mild TBI. The recruiter and PI/Site PI and co-investigators will identify potential participants through their regular contact with patients. When a clinician determines that a patient is eligible (based on study inclusion/exclusion criteria), the clinician will either approach the patient to discuss his/her interest in research, or will refer the patient to a member of the research team. The recruiter, or other co-investigators, will approach potential participants, inform them of the study, and verify their eligibility. If potential participants are interested, the recruiter will obtain written informed consent and HIPAA authorization.

It is possible that potential participants will not be able to meet in person and will need to talk to a study investigator via telephone. In this instance, a study investigator will explain the study determine that the participant is interested in participating, and screen for eligibility. If eligible, an appointment will be scheduled for the participant to meet in-person with the study team members to complete the consenting process. Or, for interested participants who reside a distance away from the VA and would like to participate in the study the ICF will be done over the telephone. After the Telephone Consent process is complete, a copy of the study ICF/Information Sheet will be mailed to the participant for his/her file. Once the consent process is completed via telephone with those participants who are not able to physically be at either the Tampa or Bay Pines VA site location, they will be asked to complete the study Baseline questionnaires. When speaking to potential participants via telephone, the study team member will be physically located at the Tampa or Bay Pines VA.

To facilitate the recruitment process, we will hang flyers throughout the hospitals and catchment area (e.g., outpatient clinics) of each hospital, and provide the clinical team with hospital-based flyers and business cards to give to interested patients. (See the Appendix for the hospital-based flyer and business card.)

Relevant Veteran Events: With permission from event organizer(s) and/or department manager(s), we will attend and/or contribute to relevant events around the Tampa/St. Petersburg area. Methods of recruitment during events may include but are not limited to, providing flyers, cards, and/or give-away recruitment materials. It may also involve giving a short presentation on the participation opportunities, collecting contact information from interested participants, or leaving a basket of give-away recruitment materials at a desk for interested participants to pick up at their leisure (the flyers, business cards, and give-away recruitment

materials are attached as an Appendix). Events and departments could include but are not limited to the University of South Florida's Veteran events and program, The Defense and Veterans Brain Injury Center events, Family Care events, Yellow Ribbon Reintegration Program Events, MacDill Air Force events, or Family/patient educational meetings. Interested participants will have the option to take recruitment materials away with them and make contact with a study team member at a later date themselves and/or leave their name, contact details, and preferred day/time with the study team member at the event who will contact them at a later date to initiate consent and enrollment. We will not be consenting participants at the Yellow Ribbon event.

Publicizing though various forms of media: We will publicize the study through various forms of media. We will contact new organizations and include new forms of media as possibilities when they are brought to our attention or as recruitment needs change. We will not submit these new organizations for IRB review but will use approved methods. Future possibilities include but are not limited to the National Military Family Association, Stars and Stripes, or Military Base newspapers. Currently, we plan to publicize in Military Times, Veterans of Foreign Wars Magazine, and through social media of relevant organizations. A half page community based color advertisement (circulating between two Half Page Ads, see Appendix) will be placed in the Military Times Combined newspapers (militarytimes.com; militarytimesedge.com; Army Times, armytimes.com; Navy Times, navytimes.com, Air Force Times, airforcetimes.com; Marine Corps Times, marinecorpstimes.com). A fullpage advertisement (as per the communitybased flvers) will also be placed in the Veterans of Foreign Wars Magazine (official publication of the Veterans of Foreign Wars of the United States). Additionally, the social media mangers of the following organizations (Wounded Warrior Project, Army, Marines, National Guard, Air Force, Navy, Brain Line) will post a brief advertisement (including a link to a PDF version of the flyer) on their Social Media sites (e.g., Facebook, Twitter feeds, press release, attached in the Appendix). Please see the attached Agreements to Support Publicizing Efforts and weblinks to social media pages from the related social media managers (Appendix). At Bay Pines VAHCS, efforts will also be made to contact Veterans who subscribe to Veterans Health via Email Blasts generated by the Public Affairs Officer.

Finally, we will send letters to potential participants, identified through VA national databases (with appropriate permissions), who have been screened and evaluated for concussion within the Bay Pines or Tampa VA systems of care and who were identified through that process as having a history of concussion.

Potential participants may respond to these various publicizing efforts via the study telephone contact details. For those recruited from the community, the study team member will explain the study over the telephone, determine that the participant is interested in participating, and screen for eligibility. If eligible, the participant will complete the consent process over the telephone or an appointment will be arranged for in-person consent at the VA. After the telephone consent a copy of the ICF/Information Sheet will be mailed to the participant for his/her file. When speaking to potential participants via telephone, the study team member will be physically located at Bay Pines or Tampa VA facilities.

Participants will be reimbursed for the time spent completing the questionnaires. Payment will be provided via a check sent to the Veteran's home or through direct deposit. We will compensate participants \$20 for the time they spend completing the first assessment and \$10 for the time they spend on the second assessment. In addition, 10% of participants who complete an interview will be compensated for their time (\$10).

